7.1.5.2. Expectedness

A serious adverse event that is not included in the Adverse Reaction section of the relevant reference safety information by its specificity, severity, outcome, or frequency is considered an unexpected adverse event. The reference safety information for this study is the laquinimod Investigator's Brochure.

The sponsor's Global Patient Safety & Pharmacovigilance Department will determine the expectedness for all serious adverse events.

7.1.5.3. Reporting a Serious Adverse Event

7.1.5.3.1. Investigator Responsibility

To satisfy regulatory requirements, all serious adverse events (as described in Section 7.1.5.1) that occur during the study period (including the protocol-defined follow-up period), regardless of judged relationship to treatment with the study drug, must be reported to the sponsor by the investigator within 24 hours of becoming aware of it. Completing the serious adverse event form and reporting the event must not be delayed, even if not all the information is available. The investigator does not need to actively monitor subjects for adverse events once the study has ended. Serious adverse events occurring to a patient after the defined study period should be reported to the sponsor only if the investigator becomes aware of them.

The serious adverse event form should be sent to the Teva local safety officer (LSO) or other designated personnel (a contract research organization [CRO] in a country without a Teva LSO). Contact information is in the Clinical Study Personnel Contact Information section. The LSO will forward the report to the sponsor's Global Patient Safety & Pharmacovigilance Department.

The following information should be provided to record the event accurately and completely:

- study number TV5600-CNS-20007 (LEGATO-HD)

Clinical Study Protocol with Am 04

- investigator and investigational center identification
- patient number
- onset date and detailed description of adverse event
- investigator's assessment of the relationship of the adverse event to the study drug (no reasonable possibility, reasonable possibility)

Additional information may include the following:

- age and sex of patient
- date of first dose of study drug
- date and amount of last administered dose of study drug
- action taken
- outcome, if known
- severity
- explanation of assessment of relatedness
- concomitant therapy (including doses, routes, and regimens) and treatment of the event
- pertinent laboratory or other diagnostic test data
- medical history
- results of dechallenge/rechallenge, if known
- for an adverse event resulting in death:
 - cause of death (whether or not the death was related to study drug)
 - autopsy findings (if available)

The investigator is responsible for ensuring that the IEC/IRB is also informed of the event, in accordance with local regulations.

Each report of a serious adverse event will be reviewed and evaluated by the investigator and the sponsor to assess the nature of the event and the relationship of the event to the study drug, study procedures, and to underlying disease.

Additional information (follow-up) about any serious adverse event unavailable at the initial reporting should be forwarded by the investigational center within 24 hours of when it becomes known to the same address as the initial report.

For all countries, The sponsor's Global Patient Safety & Pharmacovigilance Department will distribute the Council for International Organizations of Medical Sciences (CIOMS) form/XML file to the LSO/CRO for local submission to the regulatory authorities and IEC/IRBs and investigators, according to regulations.

The blinding will be maintained for the people who are involved directly in the study. Therefore, in case of a suspected unexpected serious adverse reaction (SUSAR), only the LSO/CRO will receive the unblinded report for regulatory submission; the others will receive a blinded report.

Note: Although pregnancy is not a serious adverse event, the process for reporting a pregnancy is similar to that for reporting a serious adverse event (see Section 7.2).

7.1.5.3.2. Sponsor Responsibility

If a serious unexpected adverse event is believed to be related to the study drug or study procedures, the sponsor will take appropriate steps to notify all investigators participating in sponsored clinical studies of laquinimod and the appropriate regulatory authorities (and IEC/IRB, if appropriate).

In addition to notifying the investigators and regulatory authorities (and IEC/IRB, if appropriate), other measures may be required, including the following:

- altering existing research by modifying the protocol
- discontinuing or suspending the study
- altering the process of informed consent by modifying the existing consent form and informing current study participants of new findings
- modifying listings of expected toxicities to include adverse events newly identified as related to laquinimod

7.1.6. Protocol-Defined Adverse Events for Expedited Reporting

Ischemic cardiac events (such as myocardial infarction, unstable angina, acute coronary syndrome, etc), cerebrovascular events (such as cerebral arterial occlusion, cerebral ischemia, etc), and deaths should be reported to the sponsor within 24 hours, including completion of the corresponding dedicated CRF.

7.1.7. Withdrawal Due to an Adverse Event

Any patient who experiences an adverse event may discontinue treatment at any time at the discretion of the investigator. If a patient discontinues treatment wholly or in part because of an adverse event, both the adverse events page and termination page of the CRF will be completed at that time.

A complete final evaluation at the time of the patient's withdrawal (Visit 8 procedures) should be made. In addition, a blood sample will be obtained for the measurement of study drug concentrations. The patient will be monitored at the discretion of the investigator (e.g., until the event has resolved or stabilized, until the patient is referred to the care of a health care professional, or until a determination of a cause unrelated to the study drug or study procedure is made). The investigator must inform the clinical project physician/clinical leader (CPP/CL) as soon as possible of all patients who are being considered for withdrawal due to adverse events. Additional reports must be provided when requested.

If a patient discontinues treatment for multiple reasons that include adverse events, the termination page of the CRF should indicate that the withdrawal was related to an adverse event.

An exception to this requirement will be the occurrence of an adverse event which in the opinion of the investigator is not severe enough to warrant discontinuation but which requires the use of a prohibited medication, thereby requiring discontinuation of the patient. In such a case, the reason for discontinuation would be need to take a prohibited medication, not the adverse event.

7.1.8. Medical Emergencies

Medical emergencies must be reported to the individual identified in the clinical study personnel contact information section of this protocol.

Equipment, supplies, and properly skilled medical personnel must be accessible for an adverse event requiring immediate treatment.

Any dose of study drug (whether laquinimod or placebo), whether taken intentionally or unintentionally, in excess of that prescribed must be immediately reported to the sponsor. When the identification of the study drug must be known, the investigator must follow the procedures outlined in Section 3.8.

7.1.9. Medication Error and Special Situations

Any administration of study medication that is not in accordance with the study protocol should be reported on the CRF either as a violation, if it meets the violation criteria according to the protocol (Section 11.1.2), or as a deviation in the patients source documents, regardless of whether an adverse event occurs as a result. All instances of incorrect medication administration should be categorized as 'Non-Compliance to IMP'.

Types of Medication Errors and/or special situations:

1. Medication error - Any unintentional error in the prescribing, dispensing, or administration of a medicinal product while in the control of the healthcare professional, patient or consumer.
2. Overdose - Administration of a quantity of a medicinal product given per administration or cumulatively which is above the maximum recommended dose according to the authorized product information. Clinical judgment should always be applied.
3. Misuse - Situations where the medicinal product is intentionally and inappropriately used not in accordance with the authorized product information.
4. Abuse - Persistent or sporadic, intentional excessive use of medicinal products which is accompanied by harmful physical or psychological effects.
5. Off-label use - Situations where a medicinal product is intentionally used for a medical purpose not in accordance with the authorized product information.
6. Occupational exposure- Exposure to a medicinal product, as a result of one's professional or non-professional occupation.

7.1.10. Protocol Deviations Because of an Adverse Event

If a patient experiences an adverse event or medical emergency, departures from the protocol may be allowed on a case-by-case basis. After stabilization and/or treatment has been administered to ensure patient safety, the investigator or other physician in attendance must

contact the individual identified in the Clinical Study Personnel Contact Information section of this protocol as soon as possible to discuss the situation. The investigator, in consultation with the sponsor, will decide whether the patient should continue to participate in the study. Any departures from the protocol because of adverse events must be noted on the CRF and in source documents, along with the reason for such departures.

7.2. Pregnancy

To further emphasize the importance of use of acceptable contraception and avoidance of pregnancy under laquinimod exposure, and to reduce as much as possible the exposure to laquinimod if a pregnancy occurs despite all recommended measures, all women of child-bearing potential (for example women who are not postmenopausal or have not undergone surgical sterilization) and not using acceptable methods of contraception, will be instructed about the teratogenicity and potential delayed risks for a child exposed in utero to laquinimod. These subjects will be counseled about the importance of using 2 acceptable methods of contraception throughout the entire study duration and until 30 days after the last dose of treatment was administered and about the need to stop treatment immediately if pregnancy is suspected. Patients who are women of child-bearing potential must use 2 acceptable methods of contraception for 30 days prior to initiation of treatment, throughout treatment duration and until 30 days after the last dose of treatment.

Acceptable methods of birth control include: Intrauterine devices, barrier methods (condom or diaphragm with spermicide) and hormonal methods of birth control (oral contraceptive, contraceptive patch, long-acting injectable contraceptive).

The patients' understanding of the importance of preventive pregnancy measures and their ability to follow the required instructions will be ensured by the investigator.

Additionally, monthly pregnancy tests (urine dipstick and/or serum pregnancy β -hCG test, as applicable per the relevant time point) will be performed. Early terminated subjects who are in the study for the purpose of follow-up will not be required to take the pregnancy tests if the last study drug dose was taken more than 30 days prior to the visit.

All pregnancies of women participating in study and that occur during the study, or within 30 days after the last dose of treatment was administered, are to be reported immediately to the individual identified in the clinical study personnel contact information section of this protocol, and the investigator must provide the LSO/CRO with the pregnancy form. The process for reporting a pregnancy is the same as that for reporting a serious adverse event (see Section 7.1.5.3).

Any woman who becomes pregnant during the study will discontinue treatment. Subjects who become pregnant will be monitored for the outcome of the pregnancy (including spontaneous or voluntary termination. If the pregnancy continues to term, the outcome (health of the infant up to 8 weeks of age), details of birth, and presence or absence of any birth defect, congenital abnormalities, or maternal and newborn complications, will be reported to the sponsor. Any complication of pregnancy during the study and any complication of pregnancy that the investigator becomes aware of after termination from the study will be reported as an adverse event or serious adverse event, as appropriate.

If the pregnancy does not continue to term, 1 of the following actions will be taken:

- For a spontaneous abortion, report as a serious adverse event.
- For an elective abortion due to developmental anomalies, report as a serious adverse event.
- For an elective abortion **not** due to developmental anomalies, report on the pregnancy form.

7.3. Clinical Laboratory Tests

All clinical laboratory test results outside of the reference range will be interpreted by the investigator as belonging to 1 of the following categories:

- abnormal but not a clinically significant worsening
- abnormal and a clinically significant worsening

A laboratory test result that has significantly worsened (according to medical judgment) from the baseline result will be recorded on the source documentation, transcribed onto the CRF as an adverse event, and monitored as described in Section 7.1.2. An adverse event includes a laboratory or diagnostic test abnormality (once confirmed by repeat testing) that results in the withdrawal of the patient from the study, the temporary or permanent cessation of treatment with study drug, or medical treatment or further diagnostic work-up.

Clinical laboratory tests (serum chemistry and hematology) will be performed at Visits 1-4 and 6-9. Urinalysis will be performed at screening. When applicable per local requirements, patients will undergo an HIV test at screening. Also when applicable, patients will be screened for drug substances in urine and/or CDT level in blood at screening to confirm abstinence in former alcohol and/or drug abusers.

Specific laboratory tests to be performed are listed below.

7.3.1. Serum Chemistry

The following serum chemistry tests will be performed at all scheduled visits:

- calcium
- phosphorus
- sodium
- potassium
- chloride
- bicarbonate and carbon dioxide
- glucose
- blood urea nitrogen (BUN)
- creatinine (Note: Estimated creatinine clearance will be calculated at all in-clinic study visits.)
- uric acid
- ALT
- AST
- lactic dehydrogenase (LDH)
- gamma-glutamyl transpeptidase (GGT)
- alkaline phosphatase

- creatine phosphokinase (CPK)
 - In case of CPK results >ULN, troponin and creatine kinase MB isoenzyme (CK-MB) will be tested by the central laboratory.
 - In case of CPK>10×ULN, an unscheduled visit to assess urine myoglobin will be required. The following blood tests will be repeated at the unscheduled visit: CPK, blood urea nitrogen, creatinine, electrolytes including potassium, calcium, phosphate.
- total protein
- albumin
- Fibrinogen
- CRP
- pancreatic amylase
 - Lipase will be tested in case of abnormal pancreatic amylase results
- total bilirubin
 - Only if total bilirubin is elevated, the following tests will be performed:
 - direct bilirubin
 - indirect bilirubin
- lipid profile [total cholesterol, high density lipoprotein (HDL), low density lipoprotein (LDL), triglycerides] - **at baseline and Month 12 only**
- thyroid function (T3, T4, TSH) – **at baseline, Months 6 and 12 only**

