- g. Able and willing to provide written informed consent prior to any study related procedure being performed at the screening visit. Patients with a legal guardian should be consented according to local requirements.
- h. Willing to provide a blood sample for genomic CAG analysis at the screening visit.
- i. Willing and able to take oral medication and able to comply with the study specific procedures.
- j. Ambulatory, being able to travel to the study centre, and judged by the investigator as likely to be able to continue to travel for the duration of the study
- k. Availability and willingness of a caregiver, informant, or family member to provide input at study visits assessing CIBIC-Plus, CDR-SB, PBA-s, and HD-QoL. A caregiver is recommended to be someone who attends to the patient at least 2 to 3 times per week for at least 3 hours per occasion, and the suitability of the caregiver should be judged by the investigator.
- l. For patients taking allowed antidepressant medication, the dosing of medication must have been kept constant for at least 30 days before baseline and must be kept constant during the study.

Criteria for Exclusion:

Patients are excluded from participating in this study if 1 or more of the following criteria are met:

- a. Use of immunosuppressive agents, or cytotoxic agents, including cyclophosphamide and azathioprine within 12 months prior to screening
- b. Previous use of laquinimod

- c. Use of moderate/strong inhibitors of cytochrome P450 (CYP)3A4 within 2 weeks prior to randomization.
- d. Use of inducers of CYP3A4 within 2 weeks prior to randomization.
- e. Pregnant or breastfeeding.
- f. **[Revision 1]** Serum levels $\geq 2x$ upper limit of the normal range (ULN) of either alanine aminotransferase (ALT) or aspartate aminotransferase (AST) at screening.
- g. **[Revision 1]** Serum direct bilirubin which is $\geq 1.5x$ ULN at screening.
- h. **[Revision 2]** Estimated reatinine clearance < 60 mL/min at screening, calculated using the Cockcroft Gault equation: $(140 - \text{age}) \times \text{mass (kg)} \times [0.85 \text{ if female}] / 72 \times \text{serum creatinine (mg/dL)}$

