4.2. Patient Exclusion Criteria

Patients will be excluded from participating in this study if they meet any of the following criteria:

- a. Use of immunosuppressive agents, or cytotoxic agents, including cyclophosphamide and azathioprine within 12 months prior to screening
- b. Previous use of laquinimod
- c. Use of moderate/strong inhibitors of CYP3A4 within 2 weeks prior to randomization.
- d. Use of inducers of CYP3A4 within 2 weeks prior to randomization.
- e. Pregnant or breastfeeding.
- f. **[Revision 1]** Serum levels $\geq 2 \times \text{ULN}$ of either ALT or AST at screening.
- g. **[Revision 1]** Serum direct bilirubin which is $\geq 1.5 \times \text{ULN}$ at screening.
- h. **[Revision 2]** Estimated creatinine clearance < 60 mL/min at screening, calculated using the Cockcroft Gault equation:
 $(140 - \text{age}) \times \text{mass (kg)} \times [0.85 \text{ if female}] / 72 \times \text{serum creatinine (mg/dL)}$
- i. **[Revision 1]** Subjects with a clinically significant or unstable medical or surgical condition that may put the patient at risk when participating in the study or may influence the results of the study or affect the patient's ability to take part in the study, as determined by medical history, physical examinations, ECG, or laboratory tests. Such conditions may include:
 1. A major cardiovascular event (e.g. myocardial infarction, acute coronary syndrome, de-compensated congestive heart failure, pulmonary embolism, coronary revascularization, angina) that occurred prior to randomization.
 2. Significant cardiovascular risk factors (such as, but not limited to, uncontrolled hypertension, uncontrolled diabetes), per investigator discretion.
 3. Any acute pulmonary disorder
 4. A CNS disorder other than HD that may jeopardize the subject's participation in the study, including such disorders that are demonstrated on the baseline MRI (based on local read).
 5. A gastrointestinal disorder that may affect the absorption of study medication.
 6. Acute or chronic renal disease including acute kidney injury (AKI).
 7. Any form of acute or chronic liver disease.
 8. Known human immunodeficiency virus positive status. Patients will undergo an HIV test at screening per local requirements, if applicable.
 9. Any malignancies, excluding basal cell carcinoma, in the 5 years prior to randomization.

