APPENDIX A. GUIDANCE ON SAFETY MONITORING

1. Guidance on Monitoring Subjects with Elevated Liver Function Tests

Liver enzymes (ALT, AST, GGT, ALP), as well as total bilirubin⁴ will be measured at each study visit.

In any case of elevated ALT or AST to a level exceeding of $\geq 2x$ ULN (including subjects whose baseline ALT or AST levels are $\geq 2x$ and $\leq 3x$ the ULN, who may be enrolled in the study), a thorough medical history and physical examination with a focus on liver disease should be undertaken⁵. In addition, the subject should be instructed to refrain from alcoholic beverages.

In case of symptoms compatible with drug-induced liver injury, the subject should be invited for an unscheduled visit to measure liver enzymes as soon as possible.

Solitary elevations of total bilirubin, not accompanied by elevations of ALT or AST should be managed according to the discretion of the Treating Physician.

1.1. Elevation of Either ALT or AST to ≥ 3 x ULN:

Confirmation of the abnormality (in case the abnormality is of ALT or AST ≥ 8 times the ULN, no confirmation is required prior to study drug discontinuation, but the assessments below should be performed):

- The day in which the abnormal value is received from the laboratory will be considered as Day 0.
- The Investigator should repeat the test before Day 2, for confirmation purposes (this may be performed in a local laboratory along with CBC and differential to assess for eosinophilia. In general, in case a blood sample is sent to a local laboratory, the following assessments [and reference ranges] are mandatory: ALT [serum glutamic pyruvic transaminase; SGPT], AST [serum glutamic oxaloacetic transaminase; SGOT], ALP, total bilirubin, CBC [with differential for eosinophil count, separate tube], and INR [separate tube; not to be sent in a confirmatory test]). The investigator should also question the subject regarding symptoms.

The abnormality will be regarded as confirmed in each of the following scenarios:

1. In case baseline value was within normal range and ALT or AST is still $\geq 3x$ ULN
2. In case baseline value was above ULN and ALT or AST is ≥ 2 times the baseline value.

Upon confirmation of the abnormality as noted above, the following additional evaluations should be performed and results should be recorded in the eCRF.

⁴ In case total bilirubin is $>ULN$, then direct bilirubin will be checked.

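### Exclusion (g) needs a screening direct bilirubin value, but the laboratory plan measures direct bilirubin only when total bilirubin is elevated, so (g) cannot be assessed as written in patients with normal total bilirubin

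*Protocol*

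**What the plan says.** Exclusion (g) appears with the same limit in the synopsis and in Section 4.2, where it reads "Serum direct bilirubin which is $\geq 1.5 \times \text{ULN}$ at screening". It is a rule about the direct fraction and sets no condition on total bilirubin.

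The measurement is governed by Section 7.3.1. Its list opens with "The following serum chemistry tests will be performed at all scheduled visits" and includes total bilirubin for all patients. Under that entry, direct and indirect bilirubin are subject to a condition: "Only if total bilirubin is elevated, the following tests will be performed". Section 7.3 confirms that screening is covered: "Clinical laboratory tests (serum chemistry and hematology) will be performed at Visits 1-4 and 6-9".

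Appendix A, item 1, footnote 4 repeats the condition: when total bilirubin is above ULN, "then direct bilirubin will be checked". The screening procedures in Section 3.11.1 call for clinical laboratory tests in general terms and add no separate direct bilirubin test.

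**The concern.** An eligibility criterion can be applied only if its variable is measured in every candidate. Here the stated testing rule withholds the variable from everyone whose total bilirubin is normal. Direct bilirubin is a component of total bilirubin with its own, lower reference limit, so it can be well above that limit while the total stays in range.

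The consequence concerns safety and consistent eligibility, not inference. Section 1.4.1.6 counts restricting excess drug exposure from impaired liver function among the protocol's risk mitigations, and the summary of changes for Amendment 04 explains the revision of (g) as making a hepatic criterion more stringent. A criterion tightened for that purpose is not operational in part of the population it addresses. The protocol also does not say how a site should record (g) when no direct value exists, so sites have no common rule.

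**Working it through.** No figure in the protocol needs reproducing. The check sets the passages side by side and then asks whether the reflex rule could be harmless.

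**Passages compared**

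| Item | Where | Content |
|---|---|---|
| Eligibility rule | Synopsis; Section 4.2 (g) | Direct bilirubin at or above 1.5 × its ULN at screening excludes |
| Testing rule | Section 7.3.1 | Total for all; direct only if total is elevated |
| Visits covered | Sections 7.3 and 7.3.1 | All scheduled visits, Visit 1 included |
| Repeat of testing rule | Appendix A, footnote 4 | Direct checked if total is above ULN |
| Screening list | Section 3.11.1 | No separate direct bilirubin test |
| Direct bilirubin without the condition | Appendix A, 1.1.1 and 1.1.2 | Only in on-study follow-up of confirmed ALT or AST elevation |

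The last row cannot serve eligibility, because that testing comes after randomization.

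**When would the reflex rule be harmless?** Write D and T for direct and total bilirubin, U_D and U_T for their upper limits. Since direct is part of total, D ≤ T.

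- (g) is met when D ≥ 1.5 × U_D.
- The direct test is run only when T > U_T.
- A patient falls in the gap when D ≥ 1.5 × U_D and T ≤ U_T.

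Because D ≤ T, the gap is empty only if 1.5 × U_D > U_T, that is, U_D / U_T > 1 / 1.5 = 2/3.

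**Size of the gap under assumed ranges.** The documents give no reference ranges. Assume U_D of 0.2 to 0.4 mg/dL and U_T of 1.0 to 1.2 mg/dL.

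- Lowest ratio: 0.2 / 1.2 = 0.17; (g) threshold = 1.5 × 0.2 / 1.2 = 0.25 of U_T.
- Highest ratio: 0.4 / 1.0 = 0.40; (g) threshold = 1.5 × 0.4 / 1.0 = 0.60 of U_T.

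Both ratios are below 2/3, so within these assumptions the (g) threshold lies below the level of total bilirubin that would trigger the test.

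**Illustration.** With U_D = 0.3 and U_T = 1.2 mg/dL, the (g) threshold is 1.5 × 0.3 = 0.45 mg/dL. A patient with direct 0.5 and total 1.1 mg/dL meets (g), but total is not elevated and direct is never measured.

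**What (g) becomes in practice.** Followed exactly, the plan applies the conjunction of T > U_T and D ≥ 1.5 × U_D, which is looser than the written criterion.

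**The case against.** The best reply is that little is lost. ALT, AST, GGT, alkaline phosphatase, albumin and total bilirubin are all measured at Visit 1. Exclusions (f) on ALT and AST, (i)7 on liver disease and (j) on clinically significant laboratory results act on hepatic findings, and Section 3.11.1 allows routine-care results from the screening period to be used. On treatment, Appendix A sets liver monitoring and stopping rules, and its bilirubin-based stopping rule uses total bilirubin, which is always available. All of this stands and reduces the residual risk. None of it supplies the measurement that (g) requires.

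It can also be argued that a staged approach was intended, with total first and direct only if total is raised. That is possible, but (g) does not say so. Footnote 4 is weak evidence about eligibility, since it sits in monitoring guidance; Section 7.3.1 carries the point without it.

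Three stronger readings are tempting and are not supported:

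- A reader might attach the exposure increases in Section 1.3.2.1 (about 2.3-fold observed and 3.41-fold predicted for unbound drug) to the missed patients. Those figures are for moderate hepatic impairment, and nothing in the protocol equates a raised direct fraction with normal total bilirubin to that state.
- A reader might infer that sites record (g) as passed when there is no result. The protocol does not say how this is recorded.
- A reader might infer that the (g) threshold always lies below the testing trigger. That depends on the laboratory's limits and is shown only for a direct-to-total ULN ratio of at most 2/3.

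**Conclusion.** The inconsistency is real and lies in current protocol text. Exclusion (g) requires a value that the laboratory plan does not produce for patients with normal total bilirubin, so it cannot be assessed as written in them. The conclusion rests on direct bilirubin being part of total and on the laboratory's direct ULN being no more than two thirds of its total ULN. The second is an assumption, satisfied across the illustrative ratios of about 0.17 to 0.40.

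The number of patients affected cannot be derived from the documents and is probably small; the other hepatic exclusions may catch some of them. The primary endpoint, power, type I error and analysis sets are untouched. The point is worth correcting because one stated rule defeats a stated safety criterion and the repair is cheap. The numeric limit in (g) is not questioned.

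**What to change.** Reconcile exclusion (g) in the synopsis and Section 4.2 with the testing rule in Section 7.3.1 and Appendix A, footnote 4, so that the criterion and the screening panel agree. How they are brought into agreement is for the sponsor to decide.

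- If (g) is kept as stated, the Visit 1 panel must report direct bilirubin for every patient, and the reflex condition should be limited to later visits.
- If a staged test was intended, the wording of (g) must state the condition on total bilirubin.

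Either way, say how (g) is to be recorded where no direct value is available.

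The first route costs one analyte on serum already drawn at Visit 1, a change to the central-laboratory panel and a sentence of protocol text. The second costs wording only.
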